Participants in Arm A (LBC cytology screening) will experience three screening rounds in the trial - Round 1 at baseline, Round 2 at 2.5 years, and Round 3 at 5 years. Participants in Arm B (HPV screening) will experience 2 screening rounds in the trial – Round 1 at baseline, and Round 2 at 5 years.

A 10% sample of HPV negative women in each strata of Arm B will be recalled at 2.5 years for cytology testing, for safety monitoring purposes (in order to allow safety monitoring data to be accrued earlier as the trial progresses, the initial randomization to safety monitoring will be increased to 20% of all women recruited from early-mid 2016 until sufficient women to result in an average 10% ratio randomised to safety monitoring have been recruited in each strata). The women recruited for safety monitoring are additional to the women recruited for the analysis of primary outcomes; i.e. this group will not be included in the analysis for the primary endpoint.

All women presenting for cervical screening or follow-up will be enrolled in the trial. All women will be randomized but if under current follow-up will be assigned to the appropriate management branch of the arm to which they are assigned. This approach is in line with Compass providing a sentinel experience for the National Cervical Screening Program transition in 2017, in which all women will need to transition to management under new pathways. A total of 36,300 women in the birth cohorts not offered vaccination and 84,700 women in the cohorts offered vaccination, who are presenting for routine screening, will be recruited, along with additional women to bring the total number recruited to 121,000 (with the additional women representing those presenting for routine follow-up (approximately 5%) and those recruited for a safety monitoring sample (10% of HPV screen negative participants presenting for routine screening)). The sample size requirements for the trial are based on assessment of the cumulative proportion of CIN3+ (including CIN3 and invasive cervical cancer) in women who were screen-negative at baseline.

Primary Outcome

Cumulative CIN3+ (Cervical Intraepithelial Neoplasia Grade 3 or invasive cervical cancer)

The primary outcome will be cumulative CIN3+ at 5 years following a 5-year HPV exit testing round in both arms, in women randomised to the HPV arm vs. women randomised to the LBC arm, adjusted for censoring after CIN2+ treatment.

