Upon receipt and logging of the sample at VCS Pathology, individual subject allocation to one of the study arms will be performed using a computer-generated randomisation sequence in a 1:2 ratio, stratified by age at recruitment (DOB <1st July 1980 and DOB ≥ 1st July 1980) (indicating whether or not offered HPV vaccination in the publicly-funded program). Secondary randomisation at a 1:1 ratio will be performed on samples which are allocated to study arm B (HPV DNA testing) and which are found to be other oncogenic HPV positive (not HPV 16/18) – this group will be randomised to receive either an LBC or dual-stained cytology triage test. A total of 10% of women in the HPV study arm will have early recall (at 2.5 years) for LBC testing for safety monitoring, should their primary HPV test result be negative.

Neither the participant nor the practitioner will be aware of subject allocation at the time of the recruitment visit and cervical sampling. Allocation will not be concealed in the laboratory (for reasons of practicality). The study allocation and test results will be communicated to the practitioner by means of a standard laboratory reporting form which will include the appropriate follow-up recommendation.

The randomisation schedule and process will be the responsibility of the NHMRC Clinical Trials Centre which has extensive experience in developing and managing the randomisation procedure for clinical trials.

Data Analysis Plan

Pre-specified analyses will be conducted at four time points. These will be done separately for each recruitment strata, as appropriate given the timing for when recruitment for each strata matures, and are as follows:

- 1. BASELINE and 12-month follow-up analysis**
Cross-sectional analysis of results from the baseline and 12-month follow-up screening rounds, including test positivity rates, colposcopy referral rates and CIN2+ and CIN3+ detection rates (*Secondary Objectives 4 and 5*).
- 2. 2.5 YEAR SCREENING ROUND ANALYSIS (Arm A)**
Cross-sectional analysis of CIN2+ and CIN3+ rates at the 2.5-year screening round (Arm A).
- 3. 2.5 Year SAFETY MONITORING ANALYSIS (Arm B)**
Cross-sectional analysis of CIN2+ and CIN3+ rates at the 2.5-year Safety Monitoring analysis (Arm B).
- 4. 5 YEAR FOLLOW-UP Following completion of trial follow-up at 5.5 years.**

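### As literally written, the primary analysis removes a sample of HPV-negative women from Arm B only, which conflicts with intention to treat and raises Arm B's CIN3+ rate by about 0.03 to 0.06 percentage points

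*Protocol*

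**What the plan says.** The opening text of the section on primary endpoint, objectives and sample size describes the safety sample: "A 10% sample of HPV negative women in each strata of Arm B will be recalled at 2.5 years for cytology testing". It later describes the same women as "those recruited for a safety monitoring sample (10% of HPV screen negative participants presenting for routine screening". It calls them additional to the women needed for the primary outcome and states that "this group will not be included in the analysis for the primary endpoint".

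The sampling fraction is not constant: "the initial randomization to safety monitoring will be increased to 20% of all women recruited from early-mid 2016", until the average in each stratum reaches 10%.

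Under Primary Outcome, cumulative CIN3+ at 5 years is compared "in women randomised to the HPV arm vs. women randomised to the LBC arm, adjusted for censoring after CIN2+ treatment". The next paragraph specifies intention to treat, testing non-inferiority first and superiority only if non-inferiority is declared.

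The Randomisation section puts the sample differently: "A total of 10% of women in the HPV study arm will have early recall (at 2.5 years) for LBC testing for safety monitoring", and makes this recall depend on a negative primary HPV test. The Safety Monitoring Arm section speaks of allocation to that arm for 10% of women selected from the HPV arm.

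**The concern.** The primary outcome covers HPV-positive and HPV-negative women together. If the excluded group contains only HPV-negative women, the analysed Arm B holds too many HPV-positive women. Its denominator shrinks by about 9%, while its CIN3+ count shrinks by much less. No matching group leaves Arm A, and the protocol mentions neither reweighting nor removal of an equal share of HPV-positive women. Recruiting additional women restores the head count but not the mix, because the HPV-positive women who arrive with them stay in the analysis.

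What is at stake is the primary estimate itself: an upward error in the HPV arm's rate, measured against a margin of only 0.22 percentage points, in an analysis described as intention to treat.

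**Working it through.** **Inputs from the protocol.** LBC-arm CIN3+ rate 0.6%; margin 0.22 points; 97.5% confidence, read as one-sided alpha 0.025; power above 90%; 10% non-compliance; 1:2 allocation; 121,000 women, about 5% of them in routine follow-up; average safety fraction f = 10%; CIN3+ of 0.27% at 6 years in HPV-negative women (external cohort cited under Primary HPV screening).

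**Assumed, not in the protocol.** HPV positivity q = 5-12%; a lower value of 0.05% for the CIN3+ rate r− in HPV-negative women.

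**The plan's own power.** With unpooled variance and equal true rates, the LBC arm needs (1.960 + 1.282)² × 0.006 × 0.994 × 1.5 / 0.0022² = 19,422 women. With 38,844 in the HPV arm the total is 58,266, or 64,740 after dividing by 0.9. The planned 121,000 × 0.95 × 0.9 = 103,455 women (34,485 and 68,970) give 99.1% power. The stated figure of more than 90% therefore holds as a lower bound.

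**Bias formula.** With true Arm B rate R, dropping a fraction f of HPV-negative women gives

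observed rate = [R − f(1 − q)r−] / [1 − f(1 − q)].

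Example with q = 8%, r− = 0.27%, R = 0.6%: (0.006 − 0.1 × 0.92 × 0.0027) / (1 − 0.092) = 0.0057516 / 0.908 = 0.633%. The bias is +0.033 points, 15% of the margin. The HPV-positive share of the analysed arm rises from 8.0% to 0.08/0.908 = 8.8%.

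**Power formula.** Φ{[0.0022 − (observed − LBC rate)] / SE − 1.960}, with 34,485 LBC women and 68,970 × [1 − f(1 − q)] HPV women. In the example the SE is √(0.006 × 0.994/34,485 + 0.00633 × 0.99367/62,625) = 0.0523 points, so power is Φ(0.001866/0.000523 − 1.960) = 94.6%.

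| True rate, both arms | q | r− | Observed Arm B rate | Bias (points) | Share of margin | Power |
|---|---|---|---|---|---|---|
| 0.6% | 5% | 0.05% | 0.658% | +0.058 | 26% | 86.9% |
| 0.6% | 5% | 0.27% | 0.635% | +0.035 | 16% | 94.3% |
| 0.6% | 12% | 0.05% | 0.653% | +0.053 | 24% | 88.8% |
| 0.6% | 12% | 0.27% | 0.632% | +0.032 | 14.5% | 95.0% |
| 1.0% | 5% | 0.05% | 1.100% | +0.100 | 45% | 42.5% |
| 1.0% | 5% | 0.27% | 1.077% | +0.077 | 35% | 56.3% |
| 1.0% | 12% | 0.05% | 1.092% | +0.092 | 42% | 47.4% |
| 1.0% | 12% | 0.27% | 1.070% | +0.070 | 32% | 60.1% |

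At 0.6% the unbiased SE is 0.0518 points, so the bias is 0.6 to 1.1 standard errors. With the same reduced numbers but no bias, power is about 99% at 0.6% and 91% at 1.0%. The second row group matters because the Primary Outcome section says the sample remains adequate if the LBC rate exceeds 0.6%.

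**Superiority.** For true rates of 0.60% (LBC) and 0.50% (HPV) with q = 8%, power falls from 52% to 30% if 59% of Arm B's CIN3+ arises in HPV-positive women, and to 19% if 90% does.

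**Check of the weighting remedy.** Weighting the retained HPV-negative women by 1/0.9 gives q·r+ + (1 − q)(0.9/0.9)r− = R, so the true rate returns exactly. In the example r+ = (0.006 − 0.92 × 0.0027)/0.08 = 4.395%. The weighted Arm B variance is [0.08 × 0.04395 × 0.95605 + 0.92 × 0.0027 × 0.9973/0.9 + 0.08 × 0.92 × 0.04125²] / 68,970 = 9.05 × 10⁻⁸. Adding 0.005964/34,485 for the LBC arm gives an SE of 0.0513 points, against 0.0509 if nobody were excluded.

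**The case against.** The strongest reply is that the excluded group is described in two ways. A safety randomisation applied to 20% of all women recruited, a 10% draw from the whole HPV arm acted on only after a negative test, and an allocation to a safety monitoring arm all suit a flag set before the HPV result is known. If every flagged woman, HPV-positive or not, were left out, Arm B would lose a random subset and there would be no bias. This stands as a possible reading. It does not remove the point: the sentences that define the excluded group describe it twice as HPV-negative, and no sentence says that flagged HPV-positive women are dropped too.

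A second reply is that a statistical analysis plan may supply weights. That is possible, but the protocol itself fixes the exclusion beside an intention-to-treat claim, so the conflict is in this document.

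A third reply is that the bias is conservative and modest. That is largely right. With the only HPV-negative rate in the protocol, 0.27%, the bias is about 0.03 points, and at 0.6% power stays near 94-95%, above the stated bound. Secondary outcome 1, for which the protocol says the trial is powered, is not biased, because within HPV-negative women the sample is a random subset.

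**Conclusion.** On the literal text, the primary comparison is not intention to treat, and Arm B's rate is biased upward whenever CIN3+ is commoner in HPV-positive women. Under the assumed ranges the size is about 0.03-0.06 points at a true rate of 0.6%. Power falls from about 99% to 87-95% there, and from about 91% to 43-60% at 1.0%. The estimate is distorted, and true non-inferiority or superiority can be missed.

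The documents do not support four stronger inferences that a reader might draw:

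- **That the bias is certain.** The flag-before-result reading would avoid it if every flagged woman were dropped.
- **That it could produce a false claim for HPV screening.** It works in the opposite direction.
- **That it raises an error rate for declaring HPV significantly worse.** The protocol plans no such test.
- **That the bias should be computed at 20%.** That is a temporary rate within a 10% average per stratum. The changing rate matters for the weights; the protocol gives nothing from which a separate effect of recruitment period on CIN3+ could be sized.

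**What to change.** State in the protocol who is excluded, and whether the safety flag is set before or after the HPV result.

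For the primary analysis, keep all HPV-positive Arm B women and weight each retained HPV-negative Arm B woman by 1/(1 − her safety-sampling probability), calculated by stratum and recruitment period so that the 20% phase is handled correctly. This needs only the recorded sampling fractions and a variance that allows for the weights. The cost is a very slightly wider confidence interval. Simply adding the safety women back is less clean, because they had an extra test at 2.5 years.

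Alternatively, if the flag was generated and recorded for every Arm B woman before her HPV result, exclude all flagged women whatever the result. With two thirds of 121,000 women in Arm B, this gives up about 80,667 × 0.10 × q, or roughly 400 to 970 HPV-positive women for q = 5-12%. It is not available if sampling was done only among HPV-negative women.

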- The screening interval for HPV was reduced from 6 to 5 years to reflect the final recommendations for primary HPV screening in Renewal announced in April 2014 (the Renewal evaluation originally considered both 5-yearly and 6-yearly options). In order to maintain 'synchronisation' of follow-up between HPV and cytology aims in the trial, the LBC screening interval for the main trial was also reduced to 2.5 years; this is very similar to the timing of the reminder letters sent in the current program at 27 months.
- In order to simplify the randomisation process, and in line with the primary and secondary objectives of the main trial, the randomisation process has been modified so that women are initially randomised at a 1:2 randomisation allocation ratio to either LBC or primary HPV screening (relating to the primary objective to assess performance of these primary screening tests). For women randomised to HPV screening, who are positive for another oncogenic type (not 16/18), a second-stage randomisation occurs at a 1:1 allocation ratio for triage testing using either LBC or dual stained cytology (relating the secondary objective to assess the comparative sensitivity and specificity of these tests used at this point of the pathway after primary HPV testing).

- No 'verification' colposcopy will be performed in screen-negative women – in the pilot study 5% of women were referred for verification colposcopy but this component of the study was difficult to implement, compliance with referral was poor, and the sample attending non-representative.
- The pilot study, by its nature, benefited by being 'open' - with the findings available on an ongoing basis to the investigators. However, in line with best practice for RCTs, analysis related to the trial primary endpoint will be conducted only as pre-specified.

The final analysis of the pilot study baseline screening round is complete, preliminary findings were presented at HPV2015 in Lisbon in September 2015 and The Australian Society of Cytology Annual Scientific Meeting in Brisbane in October 2015. Results from the pilot were published in September 2017 [23].

COMPASS MAIN TRIAL METHODS AND DESIGN

PRIMARY ENDPOINT, OBJECTIVES AND POWER AND SAMPLE SIZE CALCULATIONS

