For the primary outcome, intention to treat analysis will be performed with closed loop testing for non-inferiority and superiority if non-inferiority is declared. Assuming a total average CIN3+ rate in the LBC arm (across unvaccinated and vaccinated women) of 0.6%, and an absolute non-inferiority margin of 0.22%, the trial will have >90% power with 97.5% confidence to detect non-inferiority for the HPV arm, allowing for a 10% non-compliance rate. This sample is adequately powered to detect this margin should the LBC rates be higher than the assumed 0.6%.

The sample size requirements for the trial are based on assessment of the cumulative proportion of CIN3+ (including CIN3 and invasive cervical cancer) in women who were screen-negative at baseline. A major impact of this study will be the value of extended screening intervals in patients who are screen-negative at baseline. Logistically, it would be difficult to randomise patients after baseline screening and as such, the cumulative 5-year CIN3+ rates in baseline screen-negative patients may no longer be strictly comparative. However, this is a critical scientific question and so the trial is powered for this secondary outcome: the cumulative proportion of CIN3+ (including CIN3 and invasive cervical cancer) in screen-negative women, adjusted for censoring after CIN2+ treatment

Secondary Outcomes

The secondary outcomes are listed below. These will be assessed separately in each recruitment strata, i.e. in women not offered publicly-funded vaccination (born on or before 30th June 1980) and in those women offered vaccination (born on or after 1st July 1980):

1. Cumulative CIN3+ in baseline screen-negative women (ITT)
Cumulative CIN3+ in women presenting for routine screening randomised to the HPV arm who were HPV-negative at baseline, vs. CIN3+ in those randomised to the LBC arm and who were LBC-negative at baseline, adjusted for censoring after CIN2+ treatment and stratified by recruitment group (date of birth \geq July 1st 1980 and $<$ 1st July 1980). Intention to treat analysis will be performed with closed loop testing for non-inferiority and superiority if non-inferiority is declared.
2. Cumulative CIN3+ in baseline screen-negative women (per protocol)

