Cumulative CIN3+ in women presenting for routine screening randomised to the HPV arm who were HPV-negative at baseline, vs. CIN3+ in those randomised to the LBC arm and who were LBC-negative at baseline and at 2.5 years, adjusted for censoring after CIN2+ treatment and stratified by recruitment group (date of birth \geq July 1st 1980 and $<$ 1st July 1980). Per-protocol analysis will be performed in women screened and followed up within a defined tolerance period according to protocol recommendations.
3. Cumulative CIN2+ in baseline screen-negative women (ITT)
Cumulative CIN2+ in women randomised to the HPV arm who were HPV-negative at baseline, vs. CIN2+ in women who were randomised to the LBC arm and were LBC-negative at baseline, adjusted for censoring after CIN2+ treatment and stratified by recruitment group (date of birth \geq July 1st 1980 and $<$ 1st July 1980).
4. Baseline CIN2+ and CIN3+
Cross-sectional outcomes for CIN 2+ and CIN3+ detection in each arm, stratified by recruitment group (date of birth \geq July 1st 1980 and $<$ 1st July 1980).
5. CIN2+ in women randomised to HPV testing at baseline with other oncogenic HPV
CIN2+ in women randomised to HPV testing at baseline who have other HPV (not 16/18), stratified by recruitment group (date of birth \geq July 1st 1980 and $<$ 1st July 1980).
6. CIN2+ and CIN3+ in women who have an abnormal test result at baseline
CIN2+ and CIN3+ in women who have an abnormal test result at baseline, adjusted for censoring after CIN2+ treatment and stratified by recruitment group (date of birth \geq July 1st 1980 and $<$ 1st July 1980).
7. CIN2+ and CIN3+ in women who were in follow-management for a previous abnormality at baseline
CIN2+ and CIN3+ in women who were in follow-management for a previous abnormality at baseline, adjusted for censoring after CIN2+ treatment and stratified by recruitment group (date of birth \geq July 1st 1980 and $<$ 1st July 1980).

Supplementary Outcomes

Compass will also be a vehicle for other sub-studies and will have the following further objectives:

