Women will be followed up through the Compass Register, operated by VCS Ltd. The Compass Register will routinely follow up cervical abnormalities through reporting of cervical cytology and histology; questionnaires to doctors and Pap test providers; phone calls to doctors; and letters and registered letters to women.

Recruitment post-Renewed National Cervical Screening Program

Conventional cervical cytology (the Pap smear) has been used in Australia for 25 years, the success of the program is demonstrated by annual incidence and mortality rates for cervical cancer that are now amongst the lowest in the world. The Renewal of the National Cervical Screening Program to introduce HPV screening in Australia in place of the Pap test is based on the best available current evidence, and is anticipated to further reduce the incidence of cervical cancer. The trial arms in Compass are reflective of the longstanding program (Arm A) and the renewed program (Arm B), and both methods for cervical screening have been established to be safe and effective.

Although Arm A in Compass is based on the current program (pre-December 2017), it uses LBC (not conventional cytology) screening followed by partial genotyping-based HPV triage for women with abnormal cytology, which is expected to be more effective than the current triage process in the national cytology-based program (which involves repeat cytology only without HPV-based triage testing). Therefore, in Compass, 'Arm A' represents best practice triaging for cytology screening.

Following the transition to the Renewed Cervical screening program, the Compass trial will continue to recruit women until the recruitment target of 121,000 women is met. Compass will continue to recruit participants in the same manner, however the as the standard recommendations for screening in Australia will change from cytology to HPV testing, women being invited to participate in the trial will need to be advised of this.

Although long term improvements in program performance are anticipated with the new program, these gains are based on participation in one or other program for a cohort's entire screening lifetime. Women in Arm A will have two LBCs instead of one HPV test and then transition to routine 5-yearly HPV tests.

Therefore, women recruited to Compass and randomized to cytology after the transition will:

- (i) Receive 'best practice' cytology/triaging for abnormal cytology;

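### Non-inferiority on the primary outcome rests on intention to treat alone, with no stated check on how far non-adherence in later rounds may dilute a deficit of HPV screening

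*Protocol*

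**What the plan says.** Under Primary Outcome, the protocol names a single analysis set for the decision: "For the primary outcome, intention to treat analysis will be performed with closed loop testing for non-inferiority and superiority if non-inferiority is declared". Non-compliance is mentioned once there, in the power statement: "the trial will have >90% power with 97.5% confidence to detect non-inferiority for the HPV arm, allowing for a 10% non-compliance rate".

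Under Secondary Outcomes, the screen-negative comparison is given a pair of analyses: item 1 by intention to treat and item 2 per protocol. For item 2, "Per-protocol analysis will be performed in women screened and followed up within a defined tolerance period". Supplementary Outcomes item 3 relaxes the adherence criteria step by step, again only in women negative at baseline. The primary outcome, which covers all randomised women, has no such pair.

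Several sections describe routes by which the two arms may receive similar care after baseline:

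- **Recruitment post-Renewed National Cervical Screening Program.** Recruitment continues after the date when "the standard recommendations for screening in Australia will change from cytology to HPV testing".
- **Procedure for managing off-protocol women.** Some Arm B women with a conventional smear, or with abnormal cytology at an early re-screen, are followed on the Arm A pathway.
- **Opting-out of the trial.** Women who opt out return to national policy, whichever arm they came from.

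**The concern.** In a superiority trial, non-adherence usually pulls the observed difference towards zero and so works against the claim. In a non-inferiority trial the same pull works in favour of it. If some women in both arms end up with similar screening, or are not screened again, an inferior strategy can look closer to its comparator than it is. Enlarging the sample for 10% non-compliance protects power but does nothing about this.

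Convergence is foreseeable. National screening changes on 1 December 2017, so any Arm A woman recruited after about 1 June 2015 (30 months earlier) reaches her 2.5-year cytology round when HPV testing is the national standard.

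The screen-negative per-protocol analyses do not fill the gap. They concern a subgroup defined by different tests in the two arms, which the protocol itself concedes may not be strictly comparable, and item 2 states no non-inferiority rule. What is at stake is the reading of a positive result: non-inferiority of 5-yearly HPV screening when followed, or only of the policy as it happened to be delivered.

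**Working it through.** **Inputs.** From Primary Outcome: cytology-arm CIN3+ rate 0.6%, absolute margin 0.22%, 97.5% one-sided confidence (z = 1.96), 10% non-compliance. From the Compass Pilot Study section: "women are initially randomised at a 1:2 randomisation allocation ratio to either LBC or primary HPV screening". Total recruitment is 121,000, so about 40,333 in Arm A and 80,667 in Arm B. All calculations use the normal approximation with unpooled variance.

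**1. The stated power.** With no true difference,

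SE = √[0.006 × 0.994 × (1/40,333 + 1/80,667)] = 0.0471%.

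Power = Φ(0.22/0.0471 − 1.96) = Φ(2.71) = 99.7%. With 10% removed (N = 108,900) it is 99.3%. The stated figure of more than 90% therefore holds. Exactly 90% would need 58,266 women, so 121,000 does not come from this calculation.

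**2. Chance of declaring non-inferiority when the full-adherence deficit equals the margin.** Take 0.60% in Arm A and 0.82% in Arm B under full adherence. Let d be the fraction by which non-adherence shrinks the difference. The expected intention-to-treat difference is 0.22% × (1 − d), and

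P(declare) = Φ(0.22% × d / SE − 1.96), with SE taken at 0.60% and 0.60% + 0.22% × (1 − d).

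For d = 0.10 and N = 121,000, the difference is 0.198%, the Arm B rate is 0.798% and SE = 0.0496%. The probability is Φ(0.022/0.0496 − 1.96) = Φ(−1.516) = 6.5%.

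| Dilution d | N = 121,000 | N = 108,900 |
|---|---|---|
| 0 (random loss only) | 2.5% | 2.5% |
| 5% | 4.1% | 4.0% |
| 10% | 6.5% | 6.2% |
| 20% (assumed) | 14.3% | 13.3% |

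The 10% row takes every non-complier to contribute no arm difference. The 20% row is an assumption, for instance 10% crossing over in each arm; the documents give no contamination rate.

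**3. Sensitivity.** At d = 0.10 and N = 121,000, the probability is 7.6% for a cytology-arm rate of 0.4% and 5.4% for 1.0%.

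**4. The as-randomised effect.** If the quantity of interest is the difference between randomised groups with whatever adherence occurs, its true value at the boundary is itself 0.22%. The test then errs 2.5% of the time. The figures in step 2 apply only to the full-adherence effect.

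**5. Power of a per-protocol analysis.** Removing 10% leaves 99.3%. Also removing the 5% follow-up women and a 10% safety sample from Arm B leaves 34,485 and 62,073 women, and power of 98.9%.

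**The case against.** The strongest reply is that intention to treat is the right analysis for a screening policy. The outcome is defined by randomised group, and for that contrast the error is 2.5%. This stands. A reader might infer that the plan's type I error is really about 6%; the documents do not support that, because the figure is measured against a different quantity and needs every non-complier to contribute no difference.

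That last condition is demanding in this design. Under Randomisation, allocation takes place once the sample reaches the laboratory, which then runs the assigned test. Non-compliance with the baseline test is close to impossible, and a later non-complier still carries the baseline contrast. This also stands, and makes 6.5% the upper end for a 10% rate.

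Contamination is restrained too. The Compass Register sends its own reminders, women outside Victoria consent to being opted out of local register correspondence, laboratory reports give arm-specific recommendations, and consent materials were updated for the transition. These measures make large dilution less likely, but no expected rate is given.

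A reader might also conclude that a per-protocol analysis should become a mandatory second gate. That goes too far. Arm A has an additional 2.5-year visit, so attendance criteria select differently by arm, and attendance may be related to CIN3+ risk.

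Finally, the unseen SAP may contain a supportive analysis. It might, but the protocol does allocate analysis sets outcome by outcome: it pairs them for the screen-negative comparison and names intention to treat alone for the primary one. That is a stated choice and can be judged as such.

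**Conclusion.** The point holds as a gap in what supports the primary claim. It is not an error in the test. As written, a non-inferiority result on the primary outcome would show that the policy as delivered met the margin, and nothing stated for that outcome shows whether the same holds for women who followed their schedule.

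For a full-adherence deficit of 0.22%, the exposure lies between 2.5% and about 6.5% at the protocol's own 10% rate, depending on what non-compliance means, which the protocol leaves undefined. The 13% to 14% figure needs dilution of 20%, for which the documents give no basis. All figures assume a 0.6% cytology-arm rate and non-adherence unrelated to risk. The matter deserves correction before the 5-year analysis, but it does not undermine the design or the stated power.

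**What to change.** Define non-compliance, and pre-specify for the primary outcome a per-protocol or adherence-adjusted analysis in all randomised women eligible for that outcome. Censoring at departure from the assigned schedule, with weighting for predictors of departure, would allow for Arm A's additional visit and for risk-related attendance better than simple exclusion. Define adherence by attendance within the window and the test received, never by the test result.

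Report the upper confidence limit from this analysis against the same 0.22% margin, beside the intention-to-treat result. State in advance that if only intention to treat meets the margin, the conclusion is limited to non-inferiority of the policy as delivered. Keep intention to treat as the primary analysis and for superiority.

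The cost is one further analysis, using screening and follow-up records already held on the Compass Register, and possibly a more qualified conclusion. Power is not a constraint for simple exclusion of 10%, at about 99%; weighting would lower it by an amount that cannot be worked out from the documents.
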